8.4.4 Serious Adverse Events (SAEs)

All SAEs as defined below and that occur after the first dose of favipiravir and up to 46 days post-dose must be reported to the Sponsor as soon as the site becomes aware of them. Any SAEs occurring more than 46 days after last study drug administration and considered at least possibly drug-related must also be reported.

8.4.5 Definition of Serious Adverse Events

An SAE is an AE from this study that results in any of the following outcomes:

- Death (**even if caused by COVID-19 all deaths are recorded as SAEs**)
- Life-threatening situation (subject is at immediate risk of death)
- Inpatient hospitalization or prolongation of existing hospitalization
- Persistent or significant disability/incapacity
- Congenital anomaly/birth defect in the offspring of a subject who received study drug

NOTE: Important medical events that may not result in death, be immediately life-threatening, or require hospitalization, may be considered an SAE when, based upon appropriate medical judgment, they may jeopardize the subject *and* may require medical or surgical intervention to prevent one of the outcomes listed in this definition.

A life-threatening AE is defined as any adverse experience that places the subject in the view of the Site Investigator, at immediate risk of death from the event as it occurred. This does not include an event that might have led to death, if it had occurred with greater severity.

“Inpatient hospitalization” means the subject has been formally admitted to a hospital for medical reasons, for any length of time with a minimum one overnight stay. Presentation and care within an emergency department does not necessarily constitute an SAE. Complications that occur during hospitalization are AEs. If a complication prolongs hospitalization, it is an SAE.

8.4.6 SAE Reporting Requirements to the Sponsor

The procedure for reporting SAEs, regardless of causal relationship, is as follows:

- Within 24 hours of the Site Investigator's knowledge of an SAE, the site must notify the Sponsor by phone call to their site monitor, medical monitor or other Sponsor representative. They should also immediately complete the AE eCRF and select "Serious".
- This initial reporting of an SAE should contain as much information as is available to the Investigator. Submission of the SAE via the EDC should not be delayed in order to collect additional information to complete the form.
- Follow-up SAE reports may be generated in cases in which additional information becomes available. Hospital records, autopsy reports, and other documents may become available and scanned copies can be provided to the Sponsor when applicable. The follow-up SAE report should describe whether the event has resolved or continues, if and how it was treated, whether the blind was broken or not, and whether the subject continued or withdrew from study participation.
- The Sponsor (or designee) will distribute completed SAE forms, which may be used to notify the IRB when applicable, via a secure internet-based document depository.
- The Site Investigator should notify the IRB of Serious Adverse Events occurring at the site and other adverse reports received from the Sponsor in accordance with reporting requirements of the governing IRB.

The Site Investigator must take all therapeutic measures necessary for resolution of the SAE. Any medications necessary for treatment of the SAE must be recorded onto the concomitant medication section of the subject's eCRF. However, treatment medication should only be recorded in the narrative description section of the SAE form.

8.5 Suspected Unexpected Serious Adverse Reactions (SUSARs)

A SUSAR carries specific and time-based reporting requirements for the Sponsor of a clinical trial. Thus, after a Site Investigator reports an SAE, the FDA expects the Sponsor will determine whether it meets the definition of a SUSAR.

A SUSAR is defined according to 3 criteria:

1. The AE is deemed a "suspected adverse reaction" if there is a reasonable possibility that the study drug caused the AE. A "reasonable possibility" means there is evidence to suggest a causal relationship between the drug and adverse event.
2. The AE is "Serious" if it meets the definition of an SAE provided in section 8.4.5
3. The AE is deemed "unexpected" if it is not listed in the Investigator's Brochure (IB) or if in the IB, has not been reported at the severity observed.

In cases where the Sponsor deems a SUSAR has occurred, it must file an IND Safety Report with the FDA. FPHU will require the assistance and cooperation of the Site Investigator and staff to provide accurate and complete information on the subject and observed SAE so that reporting requirements to the FDA can be met.

8.5.1 Reporting SUSARs to the FDA: IND Safety Reports

IND safety reports are used to submit reports of SUSARs to the FDA. There are 2 types of reports:

- A “15-day report” is used when the reported SAE is a SUSAR and requires that as much information as is available to the investigator and the sponsor, be submitted to the FDA in on the appropriate form. For US trials, the appropriate form is the FDA Form 3500A also commonly known as a “MedWatch” form.
- A “7-day report” is used when the SUSAR is considered to be fatal or life-threatening.

The 7-day and 15-day timelines begin the day that the Sponsor determines the information qualifies for reporting and are counted in calendar days – not business days. Therefore, it is important that the Site investigator carefully follow the reporting requirements described in section 8.4.6.

8.6 Clinical Laboratory Abnormalities and Other Abnormal Assessments

Laboratory abnormalities are usually not recorded as AEs unless considered to be clinically significant by the site clinician. An abnormal laboratory result will be considered an AE if it induces clinical signs or symptoms, if the abnormality is of a degree that requires active management (e.g. discontinuation of the study drug, dose modification) or when the event is requiring treatment or other therapeutic intervention (e.g. iron supplements, blood transfusion, etc.).

The Investigator will evaluate the relationship of any significantly abnormal result to protocol treatment and clinical condition, if possible. All clinically significant abnormal laboratory results will be followed until they return to normal or become stabilized.

8.7 Handling of Overdose

An overdose is defined as any dose greater than the highest daily dose included in this document. Any overdose must be recorded. If the overdose is associated with an AE, that AE must be recorded, assessed for seriousness, and reported as an SAE.

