	
less than 10 mg of oral prednisone) or immunosuppressive or immunomodulatory drugs (e.g., immunosuppressants, anticancer drugs, interleukins, interleukin antagonists or interleukin receptor blockers).
 
NOTE: Clinical screening laboratory evaluations will be performed locally by the site or site-designated laboratory. Treatment of study participants following institutional COVID-19 treatment policies or guidelines, including the use of immunomodulatory medications, is permitted. This excludes treatment with agents that have the potential for direct antiviral activity, including convalescent plasma and NO, and co-enrolment into other clinical studies that evaluate investigational agents for COVID-19.
 
 15. Subject has a serious chronic disease (e.g., human immunodeficiency virus [HIV], cancer requiring chemotherapy within the preceding 6 months, and/or moderate or severe hepatic insufficiency and/or unstable renal, cardiac, pulmonary, neurologic, vascular, or endocrinologic disease states per investigator judgement). 16. Has previously received favipiravir within the past 30 days. 17. Has renal insufficiency requiring hemodialysis or continuous ambulatory peritoneal dialysis (CAPD). 18. Has liver impairment greater than Child Pugh A. 19. Has a history of alcohol or drug abuse in the previous two years. 20. Has a psychiatric disease that is not well controlled where controlled is defined as: stable on a regimen for more than one year. 21. Has taken another investigational drug within the past 30 days. 22. Is deemed by the Investigator to be ineligible for any reason.

Randomization
	
Following consent, those subjects meeting all entry criteria will be randomized in a 1:1 ratio.
 
Treatment Arm: favipiravir + SOC
 
Control Arm: placebo + SOC
 
Randomization will be stratified by age (≥ 50 and < 50 years old) and sex.

Treatment Regimen for Favipiravir (Standard dose)
	
 • Favipiravir and placebo tablets will be administered orally. • The regimen begins with loading doses of 1800 mg BID on Day 1 (the first 24 hours of treatment at $t = 0$ and $t = 8-12$ hours) (3600

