	
mg/day). Then maintenance dosing of 800 mg BID (1600 mg/day) from Day 2 (beginning 18-24 hours after the loading dose on Day 1).
 
 • Patients with Child-Pugh liver impairment of grade A will have their maintenance dose decreased to 600 mg BID • The total duration of treatment is expected to be 10 days.

Duration of Study Participation
	
The total anticipated duration of the study for each patient is up to 28 days.

Statistical Methods
	
To address our primary objective, time until viral shedding cessation will be compared between the two treatment arms using a two-sided Wald test derived from a Cox proportional hazards model adjusted for age and sex and stratified by site. The test will be performed at the two-sided $\alpha = 0.05$ level of significance. The hazard ratio for shedding cessation will be estimated, along with its 95% confidence interval, from a Cox proportional hazards model. If the proportional hazards assumption is not met, we will consider an extended Cox model that relaxes the proportional hazards assumption. The log rank test will also be performed.
 
The distribution of viral shedding cessation will be estimated using the Kaplan-Meier method, and Kaplan-Meier curves will be presented for each treatment arm. Time to shedding cessation along with 95% confidence intervals will be presented for each treatment arm.
 
The rate of hospitalizations and ED visits will be estimated along with 95% confidence intervals by each arm. In addition, we will compare between arms the time to each of respiratory failure, hospitalization or deaths and the corresponding composite of all such events using Kaplan-Meier methods. The frequency of adverse events and serious adverse events will be tabulated by type and by treatment arm. AEs will be compared by arm using the Chi-squared test or Fisher’s exact test, as appropriate, in the safety analysis set.
 
An interim analysis for safety and overwhelming efficacy will be performed once 50% of patients have 24 hours of follow-up complete. Enrollment will pause once 50% of patients have received treatment and will remain paused until the DSMC makes their recommendation after their safety review.

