6.6 Treatment Precautions

An overdose is defined as any dose of study drug given to a subject or taken by a subject that exceeds the dose described in this document. In the event of an overdose, the subject should be treated symptomatically, and the Sponsor informed.

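### Sections 6.6 and 8.7 define overdose differently, so on Days 2-10 intake of up to 2.25 times the planned daily amount need not enter the formal overdose record

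*Combined protocol and SAP*

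**What the plan says.** Two sections of the protocol define overdose.

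- **Section 6.6 (Treatment Precautions)** defines it as "any dose of study drug given to a subject or taken by a subject that exceeds the dose described in this document". The action is that "the subject should be treated symptomatically, and the Sponsor informed". The section gives no instruction to record the event.
- **Section 8.7 (Handling of Overdose)** states: "An overdose is defined as any dose greater than the highest daily dose included in this document". It then adds: "Any overdose must be recorded". If an adverse event accompanies the overdose, "that AE must be recorded, assessed for seriousness, and reported as an SAE".

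Neither section refers to the other, and 8.7 does not tie its threshold to the study day or to the participant's assigned dose.

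The Synopsis gives the doses that set the thresholds: "The regimen begins with loading doses of 1800 mg BID on Day 1" and "Then maintenance dosing of 800 mg BID (1600 mg/day) from Day 2". For Child-Pugh A participants, the Synopsis, Section 3.1 and Section 6.1 give 600 mg BID on Days 2-10. The note to exclusion criterion 9 in Section 5.2 gives 800 mg BID for the same group.

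**The concern.** The regimen steps down sharply after Day 1, so a threshold set at the highest daily dose is far above the plan on every later day. A participant who repeated the Day 1 amount on Day 2 would have taken an overdose under 6.6 but not under 8.7. Because the recording duty sits only in 8.7, a site could properly tell the Sponsor and still make no overdose entry, while another site made one. Overdose listings would then not be comparable across the up to five sites.

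The error is conceivable. After the first, on-site dose, participants take 200 mg tablets at home, and the step is from nine tablets per dose to four. The Diary Card in Section 6.3 is described as capturing the date and time of each dose, and a tablet count is not mentioned.

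The SAE sentence in 8.7 is a second, separate problem. It asks for a seriousness assessment and then directs SAE reporting whatever the result. Section 8.4.5 defines an SAE by outcome, and overdose is not among the outcomes listed. SAE status triggers 24-hour notification (8.4.6), and SAEs are tabulated by arm (9.1, 9.7), so the classification should not depend on how a site reads one sentence.

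**Working it through.** **Inputs**

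- Day 1 load: 1800 mg BID (Synopsis, Treatment Regimen; Section 6.1).
- Days 2-10, standard: 800 mg BID (same places).
- Days 2-10, Child-Pugh A: 600 mg BID (Section 6.1), against 800 mg BID (Section 5.2).
- Tablet strength: 200 mg (Section 6.1).

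**Step 1. Reproduce the stated daily amounts.** Daily amount = 2 x BID dose.

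- Day 1: 2 x 1800 = 3600 mg, which matches the Synopsis.
- Days 2-10: 2 x 800 = 1600 mg, which matches the Synopsis.
- Child-Pugh A under 6.1: 2 x 600 = 1200 mg.

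**Step 2. Compare the 8.7 threshold with the plan for the day.** Ratio = 3600 / planned daily amount.

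| Days 2-10 plan | mg/day (tablets) | 8.7 threshold, mg/day (tablets) | Ratio | Width of gap |
|---|---|---|---|---|
| Standard | 1600 (8) | 3600 (18) | 2.25 | 2000 mg |
| Child-Pugh A, Section 6.1 | 1200 (6) | 3600 (18) | 3.0 | 2400 mg |
| Child-Pugh A, Section 5.2 | 1600 (8) | 3600 (18) | 2.25 | 2000 mg |

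The definitions differ in this way on Days 2-10, which are 9 of the 10 treatment days.

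**Step 3. Try other readings of 8.7.** The sentence sets a dose against a daily dose. If a single dose is compared with 3600 mg, the ratio to the planned 800 mg dose is 3600 / 800 = 4.5. If the threshold is taken from any regimen mentioned in the document, the Ebola regimen in Section 2.3 gives 2 x 2400 + 1200 = 6000 mg over its first three doses, and 6000 / 1600 = 3.75. Both readings are less natural, and both widen the gap. Taking the threshold as 3600 mg/day is the conservative choice.

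**Step 4. Follow an intake of 3600 mg on a maintenance day through the protocol.**

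| Section | What it requires |
|---|---|
| 6.6 | It is an overdose, read against that day's dose. Treat symptoms and inform the Sponsor. |
| 8.7 | It is not an overdose, because 3600 mg does not exceed 3600 mg. No overdose record is required. |
| 8.4.3 | Any AE that follows is recorded, with seriousness and timing relative to study drug. |
| 6.5 | Compliance with each dose is monitored and recorded under site procedures. |

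Only the overdose record itself is missing.

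**Step 5. Set the SAE sentence beside the SAE definition.** Under 8.4.5, a non-serious AE that accompanies an overdose is not an SAE. Under 8.7 read literally, it is reported as one. The documents give no rate of overdose or of overdose-related AEs, so the effect on SAE counts cannot be computed.

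**The case against.** The strongest reply is that the two sections are not alternatives. A site must follow both, and on its natural reading 6.6 already covers the band between 1600 and 3600 mg/day and requires that the Sponsor be told. Other provisions help too: the AE definition in 8.4.2 explicitly includes overdose, 8.4.3 has all AEs recorded, 6.5 has compliance with each dose recorded, and 6.4 has supplies inventoried. This stands. A reader might infer from 8.7 that such errors would escape the Sponsor or safety review. The documents do not support that.

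It can also be said that the 9-in-10 count describes days on which the definitions differ, and says nothing about likely exposure. That stands as well. Planned use on Days 2-10 is 8 x 9 = 72 tablets, which at 18 a day would last 4 days. Section 6.3 dispenses only enough to reach the next visit, although the exact quantity is not stated. Sustained intake at 2.25 times the plan would therefore tend to show up in drug accountability, and the documents give no dosing-error rate.

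On the SAE sentence, one can argue that it is shorthand for reporting the event if it proves serious, since otherwise the assessment would have no purpose, and that over-reporting errs on the cautious side. This reading is possible, but the sentence does not say it. A reader might go further and infer that SAE counts will be materially inflated. That does not follow: under 8.7 the sentence applies only above its own high threshold, so it would seldom be triggered.

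What remains is that one term has two definitions, and the only recording duty is attached to the narrower one.

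**Conclusion.** The inconsistency is real and the text is wrong as written, but the consequence is limited. On Days 2-10, intake above 1600 and up to 3600 mg/day (2.25 times the standard plan) is an overdose under 6.6 and need not be recorded as one under 8.7. At the 1200 mg/day in Section 6.1 for Child-Pugh A, the upper end is 3.0 times the plan. What is at risk is a complete and uniform overdose record; Sponsor awareness and the capture of adverse events are not at risk.

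The SAE sentence conflicts with 8.4.5 and could make classification differ between sites. That effect is not quantified and is probably small.

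The conclusion assumes that 6.6 is read against the dose planned for the day, which its wording implies but does not state, and that the highest daily dose in 8.7 means the Day 1 load of this trial's regimen. Nothing here bears on the primary endpoint, alpha, power or sample size. It is a minor point.

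**What to change.** 1. Reconcile Sections 6.6 and 8.7 into one definition of overdose, with one rule for recording it and for notifying the Sponsor. State whether the reference is the dose assigned for that day or a single ceiling, and whether it applies per dose or per day.
2. Reconcile the Child-Pugh A maintenance dose in Section 5.2 with Section 6.1, the Synopsis and Section 3.1, because it sets the reference dose for that group.
3. State in 8.7 whether an overdose-related AE is reported as an SAE only when it meets 8.4.5, or is reported on an expedited basis without being classified as an SAE.

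Which definition, dose and reporting rule to adopt is for the sponsor to decide. The cost is protocol wording. The statistical analysis does not change.

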9 STATISTICAL METHODS

Complete details of all statistical analyses, including methods for handling missing data, will be included in a formal statistical analysis plan (SAP), to be completed as soon as possible after study initiation.

9.1 General Considerations

For the primary comparison, the following will be tested:

- Null hypothesis: time to cessation of oral shedding is equal in control and treatment;
- Alternative hypothesis: time to cessation of oral shedding differs between control and treatment.

Hypothesis tests will be two sided and conducted at an overall $\alpha = 0.05$ level of significance.

The number of hospitalizations and emergency department visits will be estimated for each arm, with 95% confidence intervals. The frequency of adverse events and serious adverse events will be

tabulated by type and by treatment arm. AEs will be compared by arm using the Chi-squared test or Fisher's exact test, as appropriate, in the safety analysis set.

9.2 Sample size justification

Approximately 180 patients will be enrolled.

Assuming 1:1 randomization and the use of a two-sided log rank test at the $\alpha=0.04999$ level of significance for the final analysis, 79 events will provide 80% power to detect a hazard ratio of 2.03. This leaves $\alpha=0.00001$ to check for overwhelming efficacy after 60 participants have completed 24 hours of follow-up. Assuming the control and treatment arm median cessation of shedding is 14 and 7 days, respectively, a two-month accrual period, a two-week follow-up period after randomization of the last patient, and a drop out of 10% in the control arm, it is estimated that the total sample size required to achieve 79 events is 120 (60 patients in each arm). We assume 33% of patients will test negative for SARS-CoV-2 virus by RT-PCR on Day 1, thus the total sample size required to be randomized is 180 ($120/0.67$). The assumption of 33% is based on calculations performed after the DSMB recommended a sample size re-estimation to account for the patients who test negative at baseline and do not contribute meaningfully to the primary analysis.

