1 SYNOPSIS

Title	A Phase 2 Randomized, Double Blinded, Placebo Controlled Study of Oral Favipiravir Compared to Current Standard of Care in Subjects with Mild or Asymptomatic COVID-19
Design	
This is a Phase 2 Double Blinded, Placebo Controlled Study evaluating the efficacy, safety and pharmacokinetics of favipiravir in adult subjects with PCR-positive, mild or asymptomatic COVID-19 infections. The study is a multicenter trial that will be conducted in up to 5 sites nationwide.
 
Subjects will be randomized to receive either favipiravir + current Standard of Care (SOC) or placebo + SOC.
 
For those subjects in the favipiravir + SOC arm, the dose regimen will be 1800 mg BID favipiravir on the first dose (day 1) followed by 800 mg BID for the next 9 days (days 2-10).
 
NOTE: 600 mg BID for subjects with Child-Pugh A liver impairment on days 2-10.
 
Subjects in the SOC arm will receive placebo.
 
The total anticipated duration of the study for each patient is 28 days.

Objectives	
Primary Objective
 
To evaluate the efficacy of oral favipiravir plus SOC compared with placebo plus SOC in reducing the duration of shedding of SARS-CoV2 virus in patients with mild or asymptomatic COVID-19.
 
Secondary Objectives
 
 1. To evaluate the efficacy of oral favipiravir compared with placebo in reducing the onset or duration of symptoms, hospitalizations, or ED visits in patients with mild or asymptomatic COVID-19. 2. To assess the safety and tolerability of favipiravir in this subject population. 3. To assess the development of antibodies against SARS-CoV-2 4. To evaluate any changes in the PK profile of favipiravir and its major metabolite M1 in this subject population
Endpoints	
Primary Endpoint:
 
Time until cessation of shedding of SARS-CoV-2 virus, defined as the time in days from randomization to the first of two consecutive negative RT-PCR results of self-collected nasal swabs.
 
Secondary Endpoints
 
 1. Nucleic acid (RT-PCR) from oropharyngeal swabs collected on Days 1, 5, 10, and 28

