	
d. Agrees to stop breast-feeding prior to first dose of study drug and through seven days after completing therapy.
 
e. Has a negative urine pregnancy test at screening.
 
6. Subject agrees to maintain home or other quarantine as recommended by the study physician, except to visit the study site as required by the protocol.
 
7. Subject agrees to take daily nasal swabs (anterior nares) for Day 1 to Day 10 and Day 14, 21, and 28 using the study provided materials, and mail via FEDEX each sample on the day collected.
 
8. Subject agrees to record daily symptoms, temperature, oxygen saturation, and pulse using the study provided materials.
 
9. Subject agrees to return to the study site for follow-up visits on Day 5, 10, and 28. The study site will be staffed by trained healthcare providers wearing full personal protective equipment and study site equipment will be disinfected between patients according to the same protocols as a clinical setting. Subjects will be wearing masks, will be appropriately spaced, and the number of subjects assessed at each time will be limited.
 
10. Members of the same household may participate in the study as long as the inclusion and exclusion criteria are met.
 
Exclusion Criteria (all questions must be answered NO)
 
11. Subject has a concomitant bacterial respiratory infection as documented by a respiratory culture with microbiologic growth.
 
NOTE: Subjects on empirical antibiotic treatment for possible but unproven bacterial pneumonia, but who are positive for SARS-CoV-2, are allowed in the study.
 
12. Subject has a history of abnormalities of uric acid metabolism.
 
13. Subject has a history of hypersensitivity to an anti-viral nucleoside-analog drug targeting a viral RNA polymerase.
 
14. Subject has any of the following abnormal laboratory test results at screening:
 
a. Platelet count <100,000 cells/mm³b. Absolute lymphocyte count <500 cells/mm³c. Hemoglobin <11 g/dL for women and <12 g/dL for mend. Serum creatinine concentration $\geq 1.5 \times$ ULNe. Confirmed creatinine clearance (CrCl) < 50 mL/min by Cockcroft-Gaultf. Serum uric acid >20 mg/dLg. Subject is using adrenocorticosteroids (except topical or inhaled preparations or oral preparations equivalent to or
--	---

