9.4 Analysis Populations

The following analysis populations will be defined for the study:

The intent-to-treat (ITT) population will include all randomized patients. Patients will be analyzed according to their assigned treatment arm. All efficacy analyses will be completed in the ITT population.

The safety population will include all patients who receive study treatment. Patients will be analyzed according to actual treatment received. All safety analyses will be completed in the safety population.

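### Section 9.2: 79 events, 80% power and a hazard ratio of 2.03 do not fit together (79 events give about 86–88%), and the interim trigger reads as 60 patients in one place and 50% of a planned 180 in others

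*Combined protocol and SAP*

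**What the plan says.** Section 9.2 specifies a two-sided log-rank test, 1:1 allocation and a final-analysis alpha of 0.04999, and says that "79 events will provide 80% power to detect a hazard ratio of 2.03". The remaining 0.00001 is spent on an efficacy look once 60 participants have 24 hours of follow-up.

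The next step turns events into patients. "Assuming the control and treatment arm median cessation of shedding is 14 and 7 days, respectively", with two months of accrual, "a two-week follow-up period after randomization of the last patient" and 10% drop-out in the control arm, "it is estimated that the total sample size required to achieve 79 events is 120 (60 patients in each arm"). The 120 is then divided by 0.67 to give 180, to "account for the patients who test negative at baseline and do not contribute meaningfully to the primary analysis".

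Four other places bear on this:

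- Section 9.4: "All efficacy analyses will be completed in the ITT population", which is defined as all randomized patients.
- Synopsis, primary endpoint: "defined as the time in days from randomization to the first of two consecutive negative RT-PCR results of self-collected nasal swabs". Swabs are taken daily on Days 1–10 and then on Days 14, 21 and 28.
- Synopsis and Section 3.1: 28 days of participation per patient.
- Synopsis and Section 10: the interim look and the enrolment pause come at 50% of patients, with no base named. Planned enrolment is 180.

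**The concern.** The power sentence gives every input needed to check it, and the check fails by 11 to 16 events, which is too much for rounding. The planned 180 is built on the 79 and the 120. A reader who cannot reproduce the first step cannot tell whether the sample size rests on a slip, on an unnamed method or on an assumption left out of the text.

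The interim trigger matters in practice. It fixes when enrolment pauses, when the DSMC reviews safety and when the efficacy look is taken. After the increase to 180, the count in Section 9.2 and the percentage in the synopsis and Section 10 agree only if the base is still 120.

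**Working it through.** **Inputs, all from Section 9.2:** two-sided alpha 0.04999, 1:1 allocation, d = 79 events, HR = 2.03, stated power 80%. The normal quantiles are 1.960 and 0.842; their sum is z = 2.802 and z² = 7.849.

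**Attempt to reproduce 79 events for 80% power**

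- Schoenfeld: 4z²/(ln HR)² = 4 × 7.849/0.7080² = 62.6, so 63 events.
- Freedman: z² × [(HR + 1)/(HR − 1)]² = 7.849 × (3.03/1.03)² = 67.9, so 68 events.

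**Power with 79 events at HR 2.03**

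- Schoenfeld: Φ(√79/2 × ln 2.03 − 1.960) = Φ(1.187) = 88.2%.
- Freedman: Φ(√79 × 1.03/3.03 − 1.960) = Φ(1.061) = 85.6%.
- Simulated log-rank (60 per arm, exponential times, stopped at the 79th event, 100,000 runs): 88%. The same simulation gives about 80% with 63 events and 82–83% with 68.

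**Hazard ratio detectable with 79 events at 80% power**

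- Schoenfeld: exp(2z/√79) = 1.88.
- Freedman: (1 + z/√79)/(1 − z/√79) = 1.92.

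**Variants.** The stated medians imply HR = 14/7 = 2.00 under exponential times. At 2.00, 80% power needs 66 to 71 events and 79 events give 84–87%, so this small difference does not explain the sentence. A one-sided test gives 92–93%. Inflating 63 or 68 events for 10% loss gives 70 or 76, not 79.

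**A reading that does return 80%.** Suppose 10% of controls (6 of 60) take on the treatment-arm rate. The same simulation at 79 events and HR 2.03 then gives about 80%. Section 9.2 does not state this assumption.

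**79 events from 120 patients.** Assumptions: exponential times with the stated medians, uniform 60-day accrual, and 10% of controls contributing no events (54 controls, 60 treated).

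- 14 days each, continuous observation: 54 × 0.50 + 60 × 0.75 = 72.
- Follow-up to two weeks after the last randomization, capped at Day 28, continuous observation: 54 × 0.724 + 60 × 0.921 ≈ 94.
- The same cap, but with the actual swab days and two consecutive negatives (Day 1 taken as randomization, no test error): about 80 by simulation.

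The last is close to 79, so the stated 120 can be reached from documented inputs. Section 9.2 does not say whether that is how it was obtained. The inflation step is consistent: 120/0.67 = 179.1, rounded to 180.

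**Interim trigger.** 60/120 = 50%; 60/180 = 33%; 50% of 180 = 90.

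**The case against.** The strongest objection is that the power sentence may be right under an input it does not mention. Drop-out in the control arm only is unusual for ordinary loss to follow-up, and if those controls are taken to behave like treated patients, 79 events at HR 2.03 do give about 80%. On that reading, substituting 86–88% would replace a correct figure. Part of this stands: the sponsor should establish how the 10% was used before changing the number. It does not rescue the text, because Section 9.2 speaks of drop-out, not crossover, and attaches it to the sentence on patient numbers.

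A second objection is that any error is conservative and so harmless. For this one sentence it is conservative. A reader might go further and infer that the trial has 86–88% power, or that enrolment could be cut. The documents do not support either inference. The 79 and 120 concern patients positive on Day 1; the plan assumes that 33% are negative on Day 1 and says they add little, yet Section 9.4 keeps them in the efficacy analysis. The sample-size text also does not mention the swab schedule or the two-negatives rule.

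A reader might also infer that follow-up is undefined or that 120 is wrong. Neither holds. Accrual, the two-week period and the 28-day participation are all documented, and one combination of them gives about 80 events. What is missing is which limit was applied.

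On the interim look, Section 9.2 does give an explicit count, and the DSMB-recommended re-estimation it reports may mean that the look has already taken place. The documents do not say so, and the enrolment-pause wording still rests on an unnamed base.

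**Conclusion.** The power sentence is wrong as written. With its own inputs, 79 events give 86–88% power at HR 2.03, not 80%; 80% needs 63–68 events, and the hazard ratio detectable with 80% power at 79 events is 1.88–1.92. This rests on the standard Schoenfeld and Freedman formulas, confirmed by simulation under exponential times, and on the 10% control drop-out not altering the hazard ratio. If it does alter it, the fault is an unstated assumption rather than wrong arithmetic.

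The finding concerns that sentence. It is not an estimate of the trial's actual power and does not show the 120 or the 180 to be wrong. The gap between HR 2.00 and 2.03 is minor.

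The interim inconsistency is separate and real: 60 participants against 90 if the base is the planned 180.

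**What to change.** 1. In Section 9.2, name the method used for the event count and say whether the 10% control-arm drop-out enters the power calculation, and how.
2. If it does (for example, controls taking on the treatment-arm rate), put that assumption in the power sentence. If it does not, restate the sentence either as 79 events giving about 86–88% power at HR 2.03 or as 79 events giving 80% power at HR about 1.9.
3. State which documented follow-up limit (two weeks after the last randomization, 28 days per patient, or both) gave 79 events from 120. The event counts above are illustrations and should not be used as replacement text.
4. Say that the power figure refers to patients positive on Day 1, so that it is not read as the power of the ITT analysis.
5. Give one interim trigger in the synopsis, Section 9.2 and Section 10, as a number or as 50% of a stated base, or record that the look was already done at 60.

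The cost is a few sentences in three places and a check of the original calculation. Enrolment, alpha and the primary test do not change.
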